## Analysis Plan

### Primary Analysis:

The primary and secondary impact analysis will use regression models to establish impact. For the primary outcome, the YP-CORE summary score will be the outcome variable. A binary indicator identifying whether the UASC was allocated to treatment (scored as unity) or control (scored as zero) will be included as a main effect in the model. The coefficient for this variable will carry the impact effect as the average difference in the YP-CORE outcome between the treatment and control group. The coefficient will be significance tested with a two-tailed alpha of  $P < 0.05$ , to establish the significance of the impact effect. Additionally, further variables will also be included in the regression, including the baseline measure of YP-CORE and an identifier for the stratification group. A single level OLS regression model with an identity link and Gaussian error term, will be used, given the lack of clustering in the data and the continuous nature of the YP-CORE outcome score.

$$\hat{Y} = a + bD + \sum_j^J z_j X_j + e \quad (1)$$

Where  $\hat{Y}$  is the predicted outcome score,  $a$  is the intercept,  $b$  is the coefficient carrying the impact effect,  $D$  is the binary indicator equalling unity for the treatment group and zero for the control group, and  $z_j$  represents coefficients for the baseline measure and the 5 stratum group indicator variables, with  $X_j$  representing the baseline score and the binary indicator variables for the 5 stratum indicator variables, and  $e$  is assumed to be normally distributed.  $J$  runs from 1 to 6, with 1 representing the mean centred baseline score and 2-6 the 5 stratum indicator variables. The excluded 6th stratum will be represented in the intercept.

Residuals from the regression model will be checked for heterogeneity and adjusted using a Huber-White approach, if required. Checks for heterogeneity will include a visual inspect of the plot of the residuals against the fitted values and Leven tests.

There is the potential to increase the statistical power of the analysis further by including other predictor variables in the regression model. However, calculation of the standardised effect size will use the conditional total variance of the impact effect in its calculation. Using a minimum specification for the model means that the standardised effect size will only be conditioned on the baseline measure and the design variables. Consequently, the effect size

can be used in a meta-analysis study without concerns over comparability caused from effect sizes adjusting for different variables across different studies.

The impact estimator will be calculated using an intention to treat (ITT) analysis to maintain the integrity of randomisation in the allocation stage. This is the fundamental test of the success of the impact effect for this study. This ITT average treatment effect (ATE), however, is based on an ‘offer to treat’. In some circumstances, especially voluntary schemes, it is possible that some people offered the treatment do not participate in the treatment (non-compliers). In such cases, the ITT effect is diminished by those who have not participated. We can calculate the size of the impact effect on those who have participated using formula (2) below, which will be greater than or equal to the ITT average effect. It is also possible that some people in the control group actually receive treatment. This cross over is likely to happen in this particular study because of the over-ride option for young people in the high-risk stratum. In this case, the control group is contaminated by treatment, lowering the ITT estimate of the average treatment effect. Formula (3) below shows how we will adjust for this circumstance of dual cross overs, where the local average treatment effect is calculated as a weighted average of treatment compliers across the treatment and control groups.

in order to adjust for the presence of non-compliers in the treatment group, and assuming we can collect outcome scores for these people, we will also calculate the treatment on the treated, following equation 8 in Bloom (2006), as:

$$TT = \frac{\bar{Y}_t - \bar{Y}_c}{\bar{D}|Z=1} \quad (2)$$

Where the denominator is the proportion receiving treatment in the treatment group

There is also the potential for cross-overs from the control group to the treatment group arising from the enforcement of the over-ride option from the BRC. Consequently, we may have cases who were allocated to treatment and either received treatment as intended or, through non-compliance, did not. Similarly, we may have people allocated to the control who, as intended, received no treatment, but also those with through the override option, received treatment. In such a situation, we will also include an estimate of the Local Average Treatment Effect (LATE), also described by Bloom (2006; equation 11):

$$LATE = \frac{\bar{Y}_t - \bar{Y}_c}{(\bar{D}|Z=1) - (\bar{D}|Z=0)} \quad (3)$$

Where the denominator is the difference in treatment rate between the treatment and control group.

These three impact effect estimators offer different perspectives on the success of the intervention. In practice, the LATE probably comes closest to capturing the impact which might be expected in a roll-out, given that the control group is likely to include a potentially influential minority of high-risk young people receiving treatment who consequently increase the baseline measure of no impact in the ITT estimator.

We note that this approach assumes the average impact effect for moderate risk cases is equal to the average impact effect for high risk cases, given that we anticipate cross-over from control groups only through the over-ride option in the high risk group. There is also the possibility that all cases in the high risk strata are overridden. If the over-ride option is exercised, we will test for the influence of the high-risk strata through sensitivity testing our results, as described below.

In addition to the estimators described above, we will provide a standardised impact effect (Glass’  $\Delta$ ). With only one primary outcome, there is no need to adjust for multiple significance testing, in line with WWCS recommendations.

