### Sample Size / Minimum Detectable Effect Size Calculations

Table 4: Minimum Detectable Effect Size Calculations

|  |               |           |
|--|---------------|-----------|
| MDES (Proportion of a Standard Deviation)  |               | 0.24      |
| Proportion of Variance in Outcome Explained by Covariates  (R  ) | Child         | 0.5       |
|  | Family        | NA        |
|  | Social Worker | NA        |
| Intraclass Correlations Coefficient (ICCs)   | Family        | NA        |
|  | Social Worker | NA        |
|  | Team          | NA        |
| Alpha  |               | 0.05      |
| Power  |               | 0.8       |
| One-Sided or Two-Sided?    |               | Two-sided |
| Level of Intervention Clustering   |               | NA        |
| Average Cluster Size (if Cluster-Randomised)   |               | NA        |
| Sample Size  | Intervention  | 145       |
|  | Control       | 135       |
|  | Total         | 280       |

 This includes, and will most likely be most influenced by, a baseline measure of the outcome.

 By default we would recommend two-sided tests.

The sample size is determined through the resources available to deliver the intervention. Consequently, we have calculated the MDES based on the expected achieved sample sizes, a stratified random allocation design at the level of the UASC and the availability of a baseline measure, which assumes a pre-post correlation of 0.71, (i.e.  $R^2 = 0.5$ ). The PowerUp tool was used to calculate the sample size, using the BIRA2\_1f spreadsheet with 6 strata (4 local and 1 virtual Local Authority for low risk cases and one stratum for high risk cases) and an average block size of 47 to be allocated evenly to treatment and control groups.

It is assumed that 88% of the 280 cases will be moderate risk, i.e. 247 cases. These will be allocated 50: 50 to treatment and control, i.e. 123.5 cases per trial arm. Of the 12% assumed to be high risk (n = 33), it is assumed that 66% will be allocated to treatment (n = 22) and 34% to control (n = 11). Overall, 145 cases will be allocated to the treatment group and 135 to the control group, i.e. 52% of total cases will be in the treatment group.

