The MDES is a standardised effect size, i.e. it is measured in standard deviation units. This is advantageous when dealing with power analysis when outcome measure summary statistics such as the mean and standard deviation are unknown. We are not aware of reliable studies showing the distribution of the YP-Core among the population of interest studied here. However, to give an example of the MDES, a recent study by O'Reilly et al (2016) showed a mean score of 18.3, with a standard deviation of 7.6 among a sample of children aged 12-16 engaging for the first time with an intervention. Using these scores for illustrative purposes only, an MDES of 0.24 multiplied by the SD of 7.6 gives a score of 1.8. Given a control group mean of 18.3, we would require the intervention to produce a YP-Core mean score of 20.1, or above, in the treatment group to be detected using our design.

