## Risks

Table 7: Risk register

| Risk   | Mitigation  |
|--|---|
| Low participation by young people in My View   | The programme has and will mitigate against this (e.g., understanding cultural competency, well-connected, integrated into existing services). The evaluation will examine adoption and acceptability, including the programme reach and take up as well as the acceptability by participants and staff.
Likelihood: Medium
Impact: High  |
| Difficulty in recruiting young people participants of for interviews   | We are ensuring that the info sheet is translated, and interviews are short and concise.
We are also offering small compensation/ incentives for interviews, and only recruiting for interviews after counselling completion when there will be better trust built up
Likelihood: Low
Impact: Medium   |
| Staff and young people only want to report positive aspects of the service in IPE evaluation   | We will mitigate this through: 
 
● Independence of the evaluation team
 
● Careful discussion of consent processes and anonymity and confidentiality
 
● Use of interpreters where necessary
 
● Use of open questions, probes in semi-structured interviews
 
 Sensitively approaching data collection
Likelihood: High
Impact: Medium |
| Difficulties in carrying out My View as designed and planned by programme team (e.g., staff illness/turnover, Covid-19 regulations changing or recruitment under remote conditions, or other administrative barriers). | The programme has and will mitigate against this (e.g., virtual design, well-connected, integrated into existing services)

The IPE will capture the appropriateness of the service (including fit with professional/service norms) and the feasibility of the implementation, facilitators and barriers to implementation, and implementation strategies.
Likelihood: Low
Impact: High             |
| Unrealistic expectations by funder, programme, and/or partners on ability to detect impact and change  | We will mitigate this through: 
 
● Clear communication
 
● Strong working relationships
 
● Build-up knowledge to detect impact in future evaluations
 
 Sound design, measures, and understanding of the importance of randomisation
Likelihood: Very low
Impact: Low   |

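### Two secondary estimators are misdescribed: formula (2) is not the effect on participants once controls cross over, and contamination alone does not make the LATE the roll-out effect

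*Protocol*

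**What the plan says.** Protocol, *Primary Analysis*, makes the ITT the decisive test and describes it as the effect of an offer. It then adds two estimators.

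- **Formula (2), TT.** The arm difference divided by the proportion treated in the treatment arm. Of this the plan says "We can calculate the size of the impact effect on those who have participated using formula (2) below".
- **Formula (3), LATE.** The arm difference divided by the difference in treatment rates between arms, added for the case where controls are treated too.

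On control crossover the same section says "This cross over is likely to happen in this particular study because of the over-ride option for young people in the high-risk stratum". It nevertheless keeps TT when crossover occurs: "These three impact effect estimators offer different perspectives on the success of the intervention". It then says that "the LATE probably comes closest to capturing the impact which might be expected in a roll-out", because treated high-risk controls distort the no-treatment comparison in the ITT. *Secondary Analysis* carries all three estimators over to SWEMWBS.

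On participation, the ethics subsection on voluntary participation says that young people may decline. The risk register (*Risks*, Table 7) lists "Low participation by young people in My View" with medium likelihood and high impact.

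**The concern.** Formula (2) corrects for non-participation in the treatment arm and has no term for treated controls. It recovers the effect on participants only when control receipt is zero, and the plan expects the opposite. Nowhere does the protocol say that TT fails in that case. The LATE is added beside TT, not substituted for it. The report would then carry a figure labelled as the effect on participants that is neither that nor the effect of the offer.

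The roll-out sentence has a different gap. Contamination of the control arm is a sound reason to correct the ITT for control receipt. Formula (3) also removes the dilution from young people who were offered My View and did not take part, and the plan gives no reason for that. In a voluntary service, non-participation would continue after roll-out. The LATE is the effect in compliers, those whose receipt was changed by allocation. It leaves out decliners and also the overridden young people, who are treated in either arm and are the plan's reason for preferring it. The plan's disclosed assumption of equal effects in moderate- and high-risk cases covers that last omission but not non-uptake.

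At stake is how the secondary estimates are read in a trial intended to inform commissioning.

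**Working it through.** **The plan's own figure.** The protocol gives no value for uptake, crossover, TT or LATE. Its one quantitative anchor is the MDES of 0.24, "which assumes a pre-post correlation of 0.71" (R² = 0.5). With 6 strata of 47 (N = 282) and 52% treated, MDES = 2.81 × √(0.5 / (0.52 × 0.48 × 282)) = 2.81 × 0.0843 = 0.237, which rounds to 0.24. The sample-size inputs are therefore coherent.

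**Inputs**

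- Control arm 135, of whom 11 are high-risk (*Sample Size*). If all 11 are overridden, control receipt is p0 = 11/135 = 8.1%. This rate is an assumption. The *Randomisation* section's 0.36 allocation would give about 12 controls, or 8.9%.
- p0 could be higher. Table 7 allows for controls attending drop-in groups, and the ethics section allows the allocation to be overridden at initial assessment. I use 15% as an assumed upper value.
- Uptake p1 is not stated. I assume a range of 100% to 70%.
- The effect of treatment, L, is assumed equal for everyone.

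**Formulas under these assumptions**

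- ITT = (p1 − p0) L
- TT, formula (2) = (p1 − p0) L / p1 = (1 − p0/p1) L
- LATE, formula (3) = L
- Effect per young person offered, against no programme = p1 L

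**Results with L = 1 and p0 = 8.1%**

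| Uptake p1 | Offer effect | ITT | TT | LATE | TT below LATE | LATE above offer effect |
|---|---|---|---|---|---|---|
| 1.00 | 1.00 | 0.919 | 0.919 | 1.00 | 8.1% | 0% |
| 0.90 | 0.90 | 0.819 | 0.909 | 1.00 | 9.1% | 11% |
| 0.80 | 0.80 | 0.719 | 0.898 | 1.00 | 10.2% | 25% |
| 0.70 | 0.70 | 0.619 | 0.884 | 1.00 | 11.6% | 43% |

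The ITT falls short of the offer effect by the same fraction, p0/p1, as TT falls short of the LATE. At p0 = 15% that fraction is 15% at full uptake and 21% at 70% uptake (0.15/0.70).

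**Which of ITT and LATE is nearer to the offer effect?** The LATE misses it by (1 − p1) L and the ITT by p0 L. The ITT is nearer whenever p0 < 1 − p1. At p0 = 8.1% that means uptake below about 92%; at p0 = 15%, below 85%. At p0 = 0 the ITT equals the offer effect.

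TT can land close to the offer effect by chance (0.909 against 0.90 in the second row). There two unrelated errors cancel; it does not estimate that quantity.

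**In points.** The protocol's illustration is that "an MDES of 0.24 multiplied by the SD of 7.6 gives a score of 1.8". If the complier effect were 1.8 points in absolute size, with 80% uptake and 8.1% crossover, the offer effect would be 0.80 × 1.8 = 1.44, the ITT 0.719 × 1.8 = 1.29, TT 0.898 × 1.8 = 1.62 and the LATE 1.8.

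**The case against.** A reader might infer that the trial's headline result is overstated. The protocol does not support that. The ITT is the decisive test, the significance test is on the allocation coefficient, and the LATE is a supplement. The roll-out sentence is one hedged remark, and the protocol does not say that the LATE will be the figure put to commissioners.

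The protocol also leaves roll-out undefined. If it means the effect per participant, the LATE is right under equal effects and nothing is overstated. The plan's point about contamination is itself valid: against no programme the ITT is too low, by 8% to 12% in the table.

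A reader might also take the TT figure to be inflated or worthless. Under crossover it is biased toward zero, modestly at 8.1%, and it would stand beside formula (3), which the plan supplies for exactly this case. If no control is treated, formula (2) is correct.

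Nor is 92% a fixed threshold. It follows from one assumed crossover rate and moves to 85% at 15%, where at 90% uptake the LATE is nearer than the ITT.

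All of this stands and limits the point to secondary estimators. Two things remain. The plan attaches a participant-effect label to a formula that does not give that effect under the crossover it expects. And its reason for the roll-out reading covers contamination but not non-participation.

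**Conclusion.** The point holds for the secondary estimators of both outcomes. The ITT estimate, its test and the data collected are not affected.

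1. TT as planned is mislabelled once any control is treated and is biased toward zero by p0/p1. This follows from the formula; the figure of 8% to 12% rests on p0 = 11/135 and assumed uptake of 100% to 70%. More crossover makes it larger.
2. The roll-out reading of the LATE is not justified by the reason given. If roll-out means the effect per young person offered, the LATE overstates it by the factor 1/p1, and the ITT is nearer whenever p0 < 1 − p1. These sizes depend on uptake, which the protocol does not give, and on equal effects. At full uptake, or with roll-out read as effect per participant, there is no overstatement.

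**What to change.** In *Primary Analysis*, and by reference in *Secondary Analysis*:

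- Report formula (2) only if no control received My View. Otherwise report the LATE in its place, for both YP-CORE and SWEMWBS.
- Describe the LATE as the effect in those whose receipt of My View was changed by allocation. Delete the roll-out sentence, or qualify it by saying whether roll-out means per young person offered or per participant.
- Keep the ITT as the effect of the offer.
- If a roll-out figure per young person offered is wanted, report observed uptake × LATE and state the equal-effect assumption. Because cases without baseline or endline scores are dropped, say whether uptake is taken in the analysed sample or among all offered.

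The cost is a few sentences and one multiplication, with no new data and no change to the primary analysis. The downsides are that the roll-out figure becomes smaller whenever uptake is incomplete, and that one redundant estimator is dropped when crossover occurs.

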## Secondary Analysis

Analysis of secondary outcome follows the same approach as described above for primary outcomes. The secondary outcome will be regressed onto the treatment indicator, controlling for the appropriate baseline measure and stratification membership. The secondary outcome will be treated as continuous and an OLS regression model will be used, assuming a Gaussian error distribution. Checks for normality of errors will be made and a Huber-White adjustment made if there is any evidence of heteroscedasticity. We will also mirror the ITT average treatment effect, treatment on the treated and local average treatment effects described above and provide a standardised impact effect (Glass'  $\Delta$ ). In line with WWCS recommendations, we will not adjust for multiple significance tests for three (or less) outcomes.

## Analysis of Harms

There is a high level of heterogeneity of interventions and measures when it comes to therapeutic intervention with unaccompanied asylum seeking children, however, evidence suggests positive impacts of such interventions (Children's Society, 2018). However, there is some evidence that therapy can have harmful consequences. The Experiences and Needs of Refugee and Asylum Seeking Children in the UK Literature Review (2005) discusses the possibility of pathologising and stigmatisation of young people's as possible harmful impact of therapy. Furthermore, there are numerous sources of qualitative evidence on negative experiences of therapy, which can be potentially harmful. The findings from Curran et al. suggest that "Contextual issues, such as lack of cultural validity and therapy options together with unmet client expectations fed into negative therapeutic processes (e.g., unresolved alliance ruptures). These involved a range of unhelpful therapist behaviors (e.g., rigidity, over-control, lack of knowledge) associated with clients feeling disempowered, silenced, or devalued". This remains an under-researched area using quantitative methods.

Unintended consequences of the intervention, including harms, will be explored in the IPE. Given the positive evidence around therapeutic intervention, it is not thought that My View would inflict undue harm. Some of the issues raised above will be mitigated by appropriate eligibility and assessment processes to ensure My View is appropriate for the young people, careful selection and matching of therapists and therapies for young people, and the development of the therapeutic relationship and coping skills.

